## **Data collection**

**Quantitative data.** Evaluation data extracted from the electronic health records of patients on prescriber panels will be constructed and delivered by the Health Innovation Program (HIP) on behalf of the Wisconsin Collaborative for Healthcare Quality (WCHQ). All members of the collaborative (including UW Health) and other specially invited members (Bellin) submit patient level data extracted from health records to a central data repository (called RBS, or “Repository Based Data Submission”), which HIP is able to access through their Business Associate agreement with WCHQ. The electronic data from the WCHQ is accessed by HIP through a secure File Transfer Protocol (FTP) site that is set up by WCHQ. An FTP is a secure way of moving data from WCHQ to an outside organization such as HIP. Datasets for researchers are constructed from these identifiable datasets that have been transformed into de-identified datasets by HIP Programmers, who are not part of the study team. Patient-level data will be grouped by prescriber and clinic for this project, and prescribers and clinics will be coded so that the Programmers are able to deliver longitudinal data at the prescriber and clinic levels. The study team will not have access to a crosswalk or any other code that would allow re-identification of the de-identified dataset delivered by HIP to the research team. Datasets will be extracted and delivered from the start of the intervention to the end of the 6-month follow-up at intervention month 27. No sensitive information will be included in the analysis dataset. No individual PHI will be collected in the course of this study. Only aggregate statistical output representing groups of subjects will be released.

**Qualitative data.** The study team will conduct two sets of semi-structured interviews (exact questions will vary based on answers to other questions) using the UW sponsored HIPPA compliant WebEx. Semi-structured interviews will be conducted with two change team leaders or their designees (a total of 8 participants) selected randomly from each intervention group at each participating health system. The interviews will take place at intervention month 18 to better understand what practice facilitation activities were done at clinics, what worked and did not work, and feedback on the intervention. A second set of semi-structured interviews will be conducted with one prescriber (a total of 8 participants) selected randomly from each intervention group at each participating health system. These interviews will take place between intervention months 18-21 to better understand what peer support activities were done at clinics, what worked and did not work, what prescribers find problematic, how peer support groups helped prescribers address these issues, and feedback on the intervention. Qualitative interviews will be recorded and transcribed for analysis using WebEx’s recording and transcription feature. All identifying information will be coded and transcripts will be stored securely on a Box folder (no PHI will be uploaded to the Box folder). The recording will be destroyed after it is transcribed.

**Assessments.** This study has developed a tailoring assessment based on pilot data to test 4 moderators (existence of an opioid prescribing policy at the system level, experience of quality improvement at the clinic level, size of the clinic, and number of high dose patients) and assess other factors that affect implementation through open and closed-ended questions. At 0, 5, 9, and 21 months assessments will be administered online (via REDCap) and online or in-person surveys. If in-

person visits occur, participants will be asked to complete a hardcopy assessment. In-person assessment data will be entered into ICTR's REDCap.

*Detailed contact logs.* Research team members responsible for delivering the implementation strategies will keep detailed logs of contact with clinics and prescribers to estimate measures of adoption and implementation. All identifiable information will be de-identified by a research team member.

In the event that subjects (clinic or prescriber) choose to withdraw from the study, data that is already collected will be kept for analyses. No further data will be collected from that subject. If the clinic withdraws, all prescribers at that clinic will not have further data collected.

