### **Secondary Aims:**

- Develop an assessment of contextual factors that influence the effectiveness of different implementation strategies.

- Test 4 moderators and assess other factors that affect implementation to use to predict which implementation strategies will be most effective in different settings.
- Estimate the costs of delivering 4 different sequences and combinations of strategies, including the incremental cost effectiveness of adding facilitation and physician peer coaching.

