## **3. Selection of Subjects**

Patients are not the subject of the study. The subjects of study will be the clinic prescribers.

Prescriber panel data will be aggregated to the clinic and prescriber levels. To be included in the aggregated, de-identified prescriber panel data, patients must:

1. have a primary care provider at the clinic;
2. prescriptions for opioid therapy for at least 3 consecutive months;
3. and no cancer diagnosis or reception of hospice care.

**Clinics:** A total of 40 clinics will be recruited from primary care clinics of the two health systems: UW Health and Bellin Health. This protocol will detail the process at UW Health primary care clinics for which the HS IRB is the IRB of record. Bellin Health will follow similar procedures with oversight from the UW study coordinator.

Clinics will be eligible for the study if they:

1. are a primary care clinic (non-pediatric primary care, internal medicine, or family medicine);
2. have not received the systems consultation intervention; and
3. do not explicitly prohibit initiating opioid therapy.

**Change team:** Up to 7 team members will be recruited and consented to participate in practice facilitation. Change teams include a change team leader (likely a clinic medical director or other clinician) and supporting clinic staff such as nurse practitioners, physician assistants, registered nurses, lab technicians, and medical assistants.

**Prescribers:** de-identified patient data will be aggregated at the level of the prescriber and clinic. In this context, prescribers will be known to the study team only by the code number assigned to them by HIP. Data will be obtained only from those clinicians who:

1. are primary care physicians or other providers with prescribing privileges;
2. are not temporary providers who do not manage stable panels or patients;

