## **Randomization**

Randomization will take place at the clinic level at month 3 (practice facilitation) and month 9 (physician peer coaching). A research team member will conduct the randomization using the urn randomization program.

Randomization of clinics will take place at intervention month 3 on a 1:1 ratio to assign clinics that will receive practice facilitation plus academic detailing or academic detailing only. At intervention month 9 all clinics will be randomized on a 1:1 ratio to assign clinics who will receive the current intervention strategy plus physician peer coaching or continue the current intervention strategy for 12 months. Randomizations will be stratified on clinic's 1) health system, 2) number of patients, and 3) average MME being greater or equal to the health system's clinic average.

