## **7. Study Parameters**

**Table 1 Outcome measure by RE-AIM category**

Domain	Source	Pertains to aim:	Months* collected
Reach: # and % of patients excluded vs. participating (incl. characteristics)	EHR	PA, SA1	1-21
Effectiveness: Overall rate of opioid prescribing and average MME per clinic and provider	EHR	PA	1-21
# and % of patients completing urine drug testing (past 12 mo.)	EHR	PA	1-21
# and % of patients screened for mental health using PHQ-2 (past 12 mo.)	EHR	PA	1-21
Mental health (PHQ-9) scores for patients screening positive on PHQ-2 (past 12 mo.)	EHR	PA	1-21
Overall rate and dose of opioid-benzodiazepine co-prescribing	EHR	PA	1-21
# and % of patients with treatment agreements (past 12 mo.)	EHR	PA	1-21
# and % of opioid prescriptions above 90 MME	EHR	PA, SA1	1-21
Patient attendance at scheduled clinic visits	EHR	PA, SA2	1-21
# and % of patients prescribed buprenorphine	EHR	PA	1-21
# and % of patients with PEG-3 score (past 12 mo.)	EHR	PA	1-21
PEG-3 scores (past 12 mo.)	EHR	PA	1-21
Adoption (setting): # and % of participating clinics vs. all clinics (incl. characteristics)	HS	SA1	1-21
Adoption (staff): # and % of participating staff vs. all eligible clinic staff (incl. characteristics)	Clinic	SA1	1-21
Clinician attendance at intervention meetings	RT	SA1	1-21
Implementation: Hours of intervention received per clinic & prescriber	RT	SA1	1-21
Adaptations made to protocols during intervention period	RT	SA1	1-21
Assessment of 4 moderators: system-level opioid prescribing policy, clinic-level experience in QI, size of clinic (# patients), # and % of patients on opioid doses > 90 MME	RT; EHR	SA1	0, 5, 9, 21
Qualitative assessment of mechanisms of action & factors influencing implementation	RT	SA1	1-21
Cost of each different implementation sequence & combination	RT	SA2	1-21

Clinics will be randomized on a 1:1 ratio to either receive practice facilitation plus academic detailing or academic detailing alone at month 3. At month 9, all clinics will be randomized on a 1:1 ratio to either continue the current intervention or add physician peer coaching to the bundle of strategies. It is anticipated that up to 152 prescribers will be recruited from 40 primary care clinics among 2 healthcare systems. The intervention will last for 21 months followed by a 6 month follow-up period.

[figure not shown]

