## **8. Statistical Considerations**

### **Research Design**

Analyses will be conducted at two levels, (1) at the clinic level and (2) at the prescriber level. UW Health and Bellin Health primary care clinics will be recruited for participation in the intervention and data collection activities. All clinics and all prescribers within clinics, once randomized, will be included in the intent-to-treat sample. The primary research outcome is morphine milligram equivalent (MME) and will be available for all prescribers within all clinics that consent, regardless of intervention engagement or drop-out.

This study will use a sequential, multiple assignment randomized trial (SMART), which is a factorial design (see Figure 1). This SMART has 4 implementation strategies embedded within it.

Figure 2. Study design

**Qual assmnt:** Qualitative assessment  
**EM:** Educational meeting  
**AF:** Audit with monthly feedback reports

**R:** Randomization point  
**PF:** Practice facilitation  
**PPC:** Prescriber peer consulting

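### System-level opioid policy is listed as a moderator to be tested, but with two health systems a fixed policy cannot be separated from the system itself

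*Combined protocol and SAP*

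**What the plan says.** Section 5 (Data collection, Assessments) says the tailoring assessment will "test 4 moderators (existence of an opioid prescribing policy at the system level, experience of quality improvement at the clinic level", and then names clinic size and number of high-dose patients. Table 1 in section 7 repeats the item: "Assessment of 4 moderators: system-level opioid prescribing policy, clinic-level experience in QI". Under Secondary Aims, section 2 makes this an aim: "Test 4 moderators and assess other factors that affect implementation to use to predict which implementation strategies will be most effective in different settings". The same section gives the practical goal as a tool with which health systems can predict who benefits from which strategies.

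The number of systems is stated in several places. Section 3: "A total of 40 clinics will be recruited from primary care clinics of the two health systems: UW Health and Bellin Health". Section 7: "It is anticipated that up to 152 prescribers will be recruited from 40 primary care clinics among 2 healthcare systems". Section 8 (Research Design): "UW Health and Bellin Health primary care clinics will be recruited for participation in the intervention and data collection activities". Section 2 also gives two. Only the Abstract says three.

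The moderators are assessed repeatedly: "At 0, 5, 9, and 21 months assessments will be administered online (via REDCap"). Section 4 (Randomization) states: "Randomizations will be stratified on clinic's 1) health system, 2) number of patients", with average MME as the third factor. Section 8 gives no moderator model. The documents state neither system's policy status nor whether it changes during the trial.

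**The concern.** The policy variable belongs to the health system, and there are two systems. Clinics and prescribers are nested within systems, so the number of independent policy values is two, however many clinics are enrolled. A difference in strategy effect between policy and no-policy clinics is then a difference between UW Health and Bellin Health. It carries everything else that differs between them. One such difference is in the intervention itself: section 5 arranges peer coaches separately for each system.

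The problem could pass unnoticed. If the systems differ in policy and the analyst fits policy-by-strategy terms without system-by-strategy terms, software returns estimates and p-values labelled as policy, with no warning. Section 8 contains nothing that would prevent this. At stake is the generalization in the secondary aim. A third system consulting the tool would be advised by its policy status on evidence showing only that two particular systems differed.

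**Working it through.** The plan gives no model, degrees of freedom or power for the moderators, so there is no stated figure to reproduce. The question is whether policy terms carry any information beyond health system. The models below are ours and only illustrate the logic.

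**Inputs.** 40 clinics and two systems (section 3); four strategies (section 8, Research Design); assessments at months 0, 5, 9 and 21 (section 5); seven outcome occasions, months 3 to 21 (section 8, Statistical analysis). The split of clinics between systems is not given, so 20/20, 24/16, 28/12 and 32/8 were assumed for the fixed cases. The ranks were the same for each split.

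**Fixed policy status.** Let g = 0 or 1 indicate the system and p its policy status.

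- *Same status in both systems.* p is constant, so policy-by-strategy terms repeat the strategy terms or are zero. Rank of the strategy model: 4. After adding policy-by-strategy: 4.
- *Different status.* p = g or p = 1 − g, so policy-by-strategy lies in the span of system-by-strategy. Rank of the system-by-strategy model: 4 × 2 = 8. After adding policy-by-strategy: 8. If the system-by-strategy terms are left out, policy terms raise the rank from 4 to 8, but those four extra dimensions are the system terms.

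A second parameterization used main effects of the two randomized components and their interactions with system, with five clinics per strategy per system. It had 9 columns and rank 6, with or without the three policy terms, for all four yes/no patterns. If system is treated as a random unit, two systems leave 2 − 2 = 0 degrees of freedom for policy.

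**Three systems, as in the Abstract.** The second parameterization has 12 columns and rank 9, with or without policy, for all eight patterns. With system as a random unit, 3 − 2 = 1 degree of freedom remains.

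**Status that changes during the trial (assumed).** Suppose one system adopts a policy at some later occasion and the other has one never or always.

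| Model | Four assessment months | Seven outcome occasions |
|---|---|---|
| Strategy-by-time plus system-by-strategy | 4×4 + 4 = 20 | 4×7 + 4 = 32 |
| Adding policy-by-strategy | 24 | 36 |
| System-by-time-by-strategy | 2×4×4 = 32 | 2×4×7 = 56 |
| Adding policy-by-strategy | 32 | 56 |

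A change in one system makes policy estimable (4 added dimensions) only if nothing else altered that system's strategy effects over time. Once that is allowed, policy again adds 0. Every adoption time gave the same ranks, at splits of 20/20 and 32/8.

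**The case against.** The strongest reply concerns measurement. The assessments are surveys of clinic staff (section 5), and section 8 (Qualitative data collection and analysis) groups contextual assessments by clinic. Answers on policy could therefore vary between clinics within a system. The instrument is not shown, so this may be so. But such variation would measure whether staff believe or know of a policy, not whether the system has one, which is what section 5 names.

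The repeated assessments could record a policy change. That is true, but the plan does not say how such a change would be used, and the estimate would rest on one system and on the assumption shown above. Section 5 itself reports a pause for COVID-19, a reminder that other things changed over the period.

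Table 1 speaks of assessing the moderators, and section 8 specifies no formal test, so testing may be meant loosely. Sections 2 and 5 nevertheless both say test, for the purpose of prediction.

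Three points on the other side stand. The ranks restate a logical identity and depend on the model chosen; the conclusion does not need them. Months 0 and 5 are not outcome occasions, so the seven-occasion column is the more relevant. Keeping the item with an explicit statement that it cannot be separated from system would be a lighter change with much the same effect.

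**Conclusion.** The concern holds. With two systems and fixed policy status, moderation by system-level policy is either not estimable or identical to moderation by health system, whatever the analysis model or number of clinics. This affects one of four named moderators, in a secondary aim, together with any use of policy status in the prediction tool. The primary aim and the three moderators that vary by clinic are unaffected. The conclusion assumes two systems, as every part of the documents except the Abstract says, and a status that does not change. A third system or a change of status in one system would not, without further assumptions, allow a result to be attributed to policy. The plan should be changed, though the main comparison does not depend on it.

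**What to change.** In section 2 (Secondary Aims), section 5 (Assessments) and Table 1, take system-level policy off the list of moderators to be tested. Keep quality-improvement experience, clinic size and high-dose patients. Continue to record each system's policy status at months 0, 5, 9 and 21 as context. Report any system-by-strategy difference descriptively, as a difference between UW Health and Bellin Health that cannot be attributed to policy, and do not use policy status as a predictor in the tool.

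Stratification by health system already supports strategy comparisons within each system. They may be thin: about 20/4 = 5 clinics per strategy per system at an even split, and 8/4 = 2 in the smaller system at 32/8.

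Reconcile the Abstract's three systems with the two named elsewhere.

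The cost is wording in four places and one fewer claimed moderator, with no new data and no change to sample size or randomization. Redefining the item at clinic level is not proposed. It would change the construct and, with study activities already under way, might need data not collected at month 0; since the instrument is not shown, this cannot be settled from the documents.

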#### Physician peer consulting surveys

The study team will ask participants in the physician peer consulting intervention to take a pre- and post-session survey for each session and a final, post-session survey using UW Madison's version of Qualtrics. Surveys will ask questions about the topics prescribers want to discuss at the upcoming consultation session, how confident they are in addressing the issues discussed at the past session, and their experience with their consultant and the intervention. The surveys will only ask the participant to provide their health system and clinic they practice at so the study team will know which topics to discuss at each clinic's consulting session, understand how the consulting session was received, and make any adaptations to future consulting sessions. For this reason, health system and clinic information will not be coded or de-identified. However, the research coordinator will code health system and clinic for the analysis.

#### Privacy and Confidentiality

To mitigate the risk of breaches of confidentiality, all subjects and clinics will be assigned a code number. A list of subject and clinic code numbers will be maintained by a research team member and stored in a password-protected spreadsheet. This data will be kept on a secure, limited access, password-protected file service on ICTR's REDCap and UW's Qualtrics.

**Potential Risks:** This research is aimed at improving clinical practice related to opioid prescribing, and falls ultimately under the context of increasing patient safety. As such, the study team believes the risks to clinician subjects and individual patients are minimal, and the intervention will improve patient safety. The potential risks of participation are:

1. Staff members could feel pressured to participate in the study. Opioid prescribing is a potentially controversial topic.
2. Prescribers may be uncomfortable discussing their prescribing practices and may resist attempts to change clinical practice. To mitigate any perceived pressure to participate in the study, the research team will make it clear, through written materials and oral instructions, that staff participation in the research is completely voluntary.
3. There could be a breach of confidentiality that could result in disclosure of research data outside the study team. To prevent this, all subjects will be assigned a code number. The lists will be kept in a locked file at HIP, and will not be shown to staff. Data collected will have the

names removed and the code attached by a research team member. Project staff who have access to data will not have access to subject names.

We have taken the following measures to reduce potential risk to subjects:

1. The primary units of analysis will be the clinic and prescribers; no staff members will ever be identified in presentations or publications.
2. The research team will emphasize the idea that the current implementation study is intended to improve opioid prescribing practices.
3. To address the risk of breach of confidentiality the research team will be provided only de-identified datasets and no individual provider will be able to be ascertained from these datasets nor will any member of the study team attempt to identify providers. Any qualitative data collected will be protected as well. Hard copy data will be kept in a locked cabinet and digital data will be stored on ICTR's REDCap.

#### *UW-ICTR's Data Monitoring Committee.*

This study will use UW-ICTR's Data Monitoring Committee. UW-ICTR has established a Data Monitoring Committee (DMC) to provide a key resource for UW-Madison investigators conducting clinical research. This DMC will provide investigators services to ensure appropriate measures are in place to promote subject safety, research integrity and compliance with federal regulations and local policies for individual clinical research protocols in need of DMC review (as determined by the Principal Investigator (PI), the funding agency, the local Scientific Review Committee, or the local IRB, and for which no DMC exists). For these studies, the UW ICTR DMC will be the primary data and safety advisory group for the Principal Investigator.

The DMC is supported in its mission of safety and compliance by experienced ICTR staff to provide administrative assistance, experienced members representing a diversity of backgrounds, skills and knowledge, and the use of the Research Electronic Data Capture (REDCap) tool which provides data management functionality by allowing the development of eCRFs and surveys to support data capture. In providing oversight for the conduct of this study, the ICTR DMC will meet every 12 months during the 5-year study. Additional meetings may be scheduled as determined by the DMC or as requested by the PI. The DMC members will review protocol-specific reports created by statisticians that serve a non-voting member role on the DMC using data pulled from REDCap. These standard reports will include an overview of study objectives, a review of actual and projected accrual rates, an evaluation of patient demographics for balance of randomization, and a summary of the number and seriousness of adverse events. An interim analysis of study results may be performed and source documents may be reviewed to allow the DMC to independently judge whether the overall integrity and conduct of the protocol remain acceptable based on data provided and reported by the Principal Investigator. The DMC will make recommendations to the Principal Investigator that could include actions of continuation, modification, suspension, or termination.

This study may be temporarily suspended or prematurely terminated if there is sufficient reasonable cause. Written notification, documenting the reason for study suspension or termination, will be provided by the suspending or terminating party to The National Institute on Drug Abuse. If the study

is prematurely terminated or suspended, the PI will promptly inform the IRB and will provide the reason(s) for the termination or suspension.

Circumstances that may warrant termination or suspension include, but are not limited to:

- Determination of unexpected, significant, or unacceptable risk to subjects
- Demonstration of efficacy that would warrant stopping
- Insufficient compliance to protocol requirements
- Data that are not sufficiently complete and/or evaluable
- Determination of futility

Study may resume once concerns about safety, protocol compliance, or data quality are addressed and satisfy the applicable federal and institutional regulatory authorities.

